### 13.3 Biomicroscopy

An external magnification and biomicroscopy will be performed using a slit-lamp at all scheduled visits for both eyes as described in Section 12.1.3.

A shift table of score values will also be provided comparing each follow-up visit to the baseline. Additionally, discrete summaries will be provided by region, finding, visit, and eye (study eye and fellow eye) for the number of subjects with at least one severity grade increase from baseline and for the number of subjects judged to be clinically significant by the Investigator. A subject listing of biomicroscopy will also be provided.

#### **13.4 Intraocular Pressure**

IOP will be collected at all scheduled visits for both eyes using an Applanation Tonometer. Two or three results (when IOP difference between test 1 and test 2 is more than 2 mmHg in one or both eyes) will be collected for both eyes. Mean IOP (mean when two results are collected or median IOP when three results are collected) will be calculated and summarized. The mean IOP and change from baseline mean IOP will be summarized for each eye (study eye and fellow eye) using continuous summary statistics by visit for each treatment group. A subject listing of IOP will also be provided.

#### **13.5 Ophthalmoscopy**

A dilated ophthalmoscopy at Screening visit and Week 8 and an undilated ophthalmoscopy at Baseline visit and Weeks 2 and 4 of the retina, macula, choroid, optic nerve, and vitreous humour will be performed. The results will be graded as normal, abnormal CS, or abnormal NCS.

A shift table will also be provided comparing each follow-up visit to baseline. A subject listing of ophthalmoscopy will also be provided.

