6.8.2 Ophthalmoscopy

Indirect ophthalmoscopy will be performed with pupil dilation at the Screening and Week 8/Exit Visits and without dilation at all other visits. The Investigator will make observations of the vitreous, retina, macula, choroid and optic nerve. Please refer to the Study Procedure Manual for more details.

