7.1 Screening Visit (Day -8 to -1)

- Informed consent
- Inclusion and exclusion criteria
- Demographics
- Medical, ophthalmic, and surgical history
- Prior or concomitant medication review
- Vital signs (heart rate and blood pressure only)
- Ocular symptoms and AE review for both eyes
- BCVA using the ETDRS method and following manifest refraction for both eyes
- Anterior segment biomicroscopic examination of both eyes
- CCT will be measured by ultrasound pachymetry in both eyes
 - Note: Ultrasound pachymetry should be performed at approximately the same time of day for all visits (\pm 60 minutes) and always before noon (local time)
- IOP in both eyes
- Dilated Ophthalmoscopy in both eyes
- Tomography (Pentacam[®]) for both eyes (at selected sites only) – may be performed prior to ophthalmoscopy while the subject is dilating

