7.2 Treatment Period

7.2.1 Baseline (Day 1) Procedures

- Inclusion and exclusion criteria
- Visual Function and Corneal Health Status (V-FUCHS) patient reported visual disability questionnaire ([Wacker 2018](#))
- Medical, ophthalmic, and surgical history
- Concomitant medication review
- Vital signs (heart rate and blood pressure only)

- Urine pregnancy test (WOCBP only)
- Ocular symptoms and AE review for both eyes
- BCVA using the ETDRS method and following manifest refraction for both eyes
- Anterior segment biomicroscopic examination of both eyes
- CCT will be measured by ultrasound pachymetry in both eyes
 - Note: Ultrasound pachymetry should be performed at approximately the same time of day for all visits (\pm 60 minutes) and always before noon (local time)
- IOP in both eyes
- Ophthalmoscopy without dilation in both eyes
- Tomography (Pentacam[®]) for both eyes (at selected sites only)
- Study eye determination (See Section 4.4)
- Randomization
- Eye drop instruction and demonstration for the study eye
- Dispensing of study medication, Study Artificial Tears (if randomized to the QD dosing arm), and Protocol Approved Artificial Tears

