7.2.4 Week 8 (Day 56 ± 3) or Early Termination Procedures

- Visual Function and Corneal Health Status (V-FUCHS) patient reported visual disability questionnaire (Wacker 2018)
- Concomitant medication review
- Vital signs (heart rate and blood pressure)
- Urine pregnancy test (WOCBP only)
- Ocular symptoms and AE review for both eyes
- BCVA using the ETDRS method and following manifest refraction for both eyes

- Anterior segment biomicroscopic examination of both eyes
- CCT will be measured by ultrasound pachymetry in both eyes
 - Note: Ultrasound pachymetry should be performed at approximately the same time of day for all visits (\pm 60 minutes) and always before noon (local time)
- IOP in both eyes
- Dilated ophthalmoscopy in both eyes
- Tomography (Pentacam[®]) for both eyes (at selected sites only) – may be performed prior to ophthalmoscopy while the subject is dilating

The Week 8 Visit will be the final visit, and the subject should be thanked for their participation in the study.

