### **8.2 Missing or Inconclusive Data Handling**

#### **8.2.1 ASSESSMENT WINDOWS**

Assessment window mapping will be applied to both efficacy and safety outcomes for table summaries using observed data only (ODO). Unscheduled or early termination visits that are within the protocol specified window of a scheduled visit will be mapped to that visit to replace the missing scheduled visit. Missing data handling for efficacy variables as described in Section 8.2.2 will be applied after assessment window mapping. Both the actual visit and windowed visit will be displayed in the listings.

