### 8.3 Definition of Baseline

Baseline is defined as the last measurement (including measurement from unscheduled visits) prior to the first dose of study medication. The date of first dose of study medication is assumed to be same as the first study medication dispensation date.

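### The Week 8 ophthalmoscopy shift sets a dilated exam against the undilated Day 1 exam, so a pre-existing finding can be tabulated as new; the dilated Screening exam is the like-for-like reference

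*SAP*

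**What the plan says.** Two kinds of exam are planned. Protocol 6.8.2 states: "Indirect ophthalmoscopy will be performed with pupil dilation at the Screening and Week 8/Exit Visits and without dilation at all other visits". SAP 13.5 repeats the split: "A dilated ophthalmoscopy at Screening visit and Week 8 and an undilated ophthalmoscopy at Baseline visit and Weeks 2 and 4". The visit lists agree: "Dilated Ophthalmoscopy in both eyes" at Screening (Protocol 7.1), "Ophthalmoscopy without dilation in both eyes" on Day 1 (Protocol 7.2.1), and "Dilated ophthalmoscopy in both eyes" at Week 8 or early termination (Protocol 7.2.4).

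SAP 8.3 gives one baseline rule for all assessments: "Baseline is defined as the last measurement (including measurement from unscheduled visits) prior to the first dose of study medication". First dose is taken as the dispensation date, which is Day 1. SAP 13.5 grades results as normal, abnormal and clinically significant, or abnormal and not clinically significant. It then adds: "A shift table will also be provided comparing each follow-up visit to baseline". Tables 14.3.3.4.1 (study eye) and 14.3.3.4.2 (fellow eye) carry this out.

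For visit mapping, SAP 8.2.1 says: "Unscheduled or early termination visits that are within the protocol specified window of a scheduled visit will be mapped to that visit". This covers safety as well as efficacy summaries and applies where the scheduled visit is missing.

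Neither document makes Screening the Week 8 reference or mentions the change of method between the two exams being compared. SAP 15, which lists departures from the protocol's analyses, is silent on it.

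**The concern.** A shift table is read as change in the eye. Here the Week 8 column mixes change in the eye with change in how the eye was examined. If dilation shows vitreous, macular or peripheral findings that an undilated view misses, a finding that was there before dosing can move from normal to abnormal with nothing having happened. The eyes were selected for corneal edema.

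Safety is a secondary objective, and Week 8 is the last fundus assessment, at the longest exposure. Neither arm is untreated, so the within-arm count of normal-to-abnormal shifts is what a reader would look at. A finding could be recorded at Screening, not seen on Day 1 and seen again at Week 8. The trial's own data would then contradict its table.

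**Working it through.** **Tracing the rules.** The plan states no figure on this point, so the check follows the schedule and the baseline definition.

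| Follow-up exam | Method | Reference under SAP 8.3 | Like for like? |
|---|---|---|---|
| Week 2 | undilated | Day 1, undilated | yes |
| Week 4 | undilated | Day 1, undilated | yes |
| Week 8/Exit | dilated | Day 1, undilated | no |
| Early termination mapped to Week 2 or 4 | dilated | Day 1, undilated | no |
| Week 8 against Screening (not planned) | dilated | Screening, dilated | yes |

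The Screening window is Day -8 to -1 and there is no Day 0 (SAP 3.1), so a Screening exam in window is at most 8 days before Day 1. If a subject has no Day 1 exam, the last-measurement rule falls back to Screening.

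**Illustration of size.** The only input from the documents is up to 20 subjects per arm (SAP 5). The rest are assumptions:

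- prevalence of a pre-existing finding, p = 0.10 to 0.30
- chance that an undilated exam detects it, u = 0.40 to 0.80
- chance that a dilated exam detects it, d = 0.90
- detection independent between exams

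Expected false normal-to-abnormal shifts per 20 subjects:

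- against Day 1: 20 × p × (1 − u) × d
- against Screening: 20 × p × (1 − d) × d

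| p | u | Against Day 1 | Against Screening |
|---|---|---|---|
| 0.10 | 0.80 | 20 × 0.10 × 0.20 × 0.90 = 0.36 | 20 × 0.10 × 0.10 × 0.90 = 0.18 |
| 0.20 | 0.80 | 0.72 | 0.36 |
| 0.20 | 0.60 | 1.44 | 0.36 |
| 0.20 | 0.40 | 2.16 | 0.36 |
| 0.30 | 0.40 | 20 × 0.30 × 0.60 × 0.90 = 3.24 | 20 × 0.30 × 0.10 × 0.90 = 0.54 |

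The chance of at least one false shift among 20 subjects, 1 − (1 − rate)^20, runs from 0.30 to 0.97 against Day 1 and from 0.17 to 0.42 against Screening. If both methods detect every finding, both counts are 0.

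**Direction.** Misses at Week 8 also produce false abnormal-to-normal shifts: 20 × p × u × (1 − d) against Day 1. With p = 0.20 and u = 0.60 this is 20 × 0.20 × 0.60 × 0.10 = 0.24, against 1.44 the other way, a net 1.20 toward apparent worsening. Against Screening both directions are 20 × 0.20 × 0.90 × 0.10 = 0.36, so the net is 0. Changing the reference thus reduces the false shifts and, under these assumptions, balances those that remain.

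**The case against.** The best case against acting is that the harm is conditional, contained and partly visible already.

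- **It may not happen.** A false shift needs a Day 1 grade of normal in an eye whose finding is then seen at Week 8. The study is open-label, nothing hides the Screening result from the examiner, and ophthalmic history is taken at Screening and Baseline (Protocol 6.2). An examiner may carry a known finding forward. This stands: no passage says how Day 1 grading treats a known finding, so the consequence is a possibility.
- **There is a check.** Drug goes into the study eye only (Protocol 4.4), and both eyes have the same exams. Table 14.3.3.4.2 therefore shows the same unlike comparison in an undosed eye. A reader might infer from the lack of an untreated arm that nothing could expose the artefact; that goes too far. The check is partial, because fellow eyes may differ in edema and exclusion 3 (Protocol 4.3) screens only the eligible eye(s).
- **Eligibility limits it.** Exclusion 3 removes clinically significant disease that could interfere with interpretation. What remains in study eyes should be mostly minor, and the grading separates clinically significant findings from the rest. Lesser findings can still enter.
- **It should not reach the adverse event tables.** Unchanged or improved pre-existing conditions are not recorded as later adverse events (Protocol 6.9.1), and such events are kept out of the summaries (SAP 13.1). Listing 16.2.10 lets a reader trace a Screening finding by hand. Both points stand, but neither changes what the shift table shows.
- **One last-pre-dose baseline is a common convention.** True, and a second reference makes the table less simple. The convention suits a measurement made the same way each time, which this one is not.

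The early-termination route is marginal. It needs such a visit inside a ±3-day window with the scheduled visit missing, and the documents give no expected number.

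**Conclusion.** The point holds as a limited one. The rules as written set a dilated Week 8 exam against an undilated Day 1 exam while a dilated Screening exam goes unused. A pre-existing finding can therefore appear as a normal-to-abnormal shift in the Week 8 column of Tables 14.3.3.4.1 and 14.3.3.4.2, and occasionally in an earlier column through a mapped early-termination exam.

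Its size cannot be derived from the documents. About 0.4 to 3.2 false shifts per 20 subjects against Day 1 and 0.2 to 0.5 against Screening is an illustration that rests wholly on the assumed rates. On those values the change halves the artefact when undilated detection is 80% (0.72 to 0.36) and cuts it by five-sixths when it is 40% (2.16 to 0.36). It is largely, not wholly, removed.

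Three stronger readings are tempting and unsupported. One is that the Week 8 tables will be wrong: that needs detection rates and grading practice the documents do not give. Another is that the artefact vanishes with Screening as reference: two imperfect dilated exams can still disagree. The third is that the regimen comparison is distorted: both arms share the exam schedule, so the QD-BID contrast is not biased in a set direction. The risk is to the reading of study-eye counts within an arm. No test or efficacy endpoint depends on these descriptive tables. The change is worth making because it is cheap.

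**What to change.** In SAP 13.5, with an exception in SAP 8.3:

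- Make the reference for any dilated post-dose ophthalmoscopy the last dilated pre-dose exam, normally Screening. This covers Week 8/Exit and early-termination exams, including those mapped to Week 2 or Week 4.
- Keep the undilated Day 1 exam as the reference for the undilated Week 2 and Week 4 exams.
- Footnote Tables 14.3.3.4.1 and 14.3.3.4.2 with the reference exam used for each column, and flag any mapped early-termination exam.
- Record the change in SAP 15.

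No new data or visit is needed, and no clinical procedure changes. The cost is SAP wording, modest programming to choose the reference by exam method, and a table with two reference exams, the Week 8 one being up to 8 days older than Day 1.

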#### **13.6 Vital Signs**

Vital signs (heart rate, systolic sitting blood pressure, diastolic sitting blood pressure) will be collected at Screening, Baseline and Week 8. The results will be summarized by visit for each treatment group, using continuous summary statistics, including change from baseline. A subject listing of the vital signs results will also be provided.

### **14. Interim Analyses**

No interim analysis is planned.

### **15. Changes from Protocol-Stated Analyses**

1. Assessment window mapping will be applied for missing values at scheduled visits in the table summaries using ODO.
2. Multiple imputations by FCS regression method instead of protocol-stated monotone regression will be employed to handle missing data without withdrawal or withdrawal due to reasons other than lack of efficacy or adverse events. FCS is a valid statistical method that has greater flexibility than monotone regression method.
3. Additional exploratory efficacy endpoints are added to look at proportion of subjects with complete resolution of epithelial edema at week 4 and 8 among subjects who have epithelial edema at baseline.

## 17. Revision History

Documentation of revision to the SAP will commence after approval of the final version 1.0.

## 18. Tables

Tables that will be included in the topline delivery are shown in boldface font.

Table Number	Title	Population
Table 14.1.1	Subject Disposition	
Table 14.1.2	Demographics	Modified Intent-to-Treat Population
Table 14.1.3.1	Ocular Medical History	Modified Intent-to-Treat Population
Table 14.1.3.2	Non-Ocular Medical History	Modified Intent-to-Treat Population
Table 14.1.4.1	Ocular Prior and Concomitant Medications	Modified Intent-to-Treat Population
Table 14.1.4.2	Non-Ocular Prior and Concomitant Medications	Modified Intent-to-Treat Population
Table 14.2.1.1	Change from Baseline in Central Corneal Thickness (µm) as Assessed by Ultrasound Pachymetry at Week 4 (Study Eye)	Modified Intent-to-Treat Population (Observed Data Only)
Table 14.2.1.2	Change from Baseline in Central Corneal Thickness (µm) as Assessed by Ultrasound Pachymetry at Week 4 (Study Eye)	Modified Intent-to-Treat Population (Multiple Imputation)
Table 14.2.1.3	Change from Baseline in Central Corneal Thickness (µm) as Assessed by Ultrasound Pachymetry at Week 4 (Study Eye)	Modified Intent-to-Treat Population (LOCF)
Table 14.2.1.4	Change from Baseline in Central Corneal Thickness (µm) as Assessed by Ultrasound Pachymetry at Week 4 (Study Eye)	Per Protocol Population (Observed Data Only)
Table 14.2.1.5	Change from Baseline in Central Corneal Thickness (µm) as Assessed by Ultrasound Pachymetry by Visit	Modified Intent-to-Treat Population (Observed Data Only)
Table 14.2.1.6	Change from Baseline in Central Corneal Thickness (µm) as Assessed by Ultrasound Pachymetry by Visit	Per Protocol Population (Observed Data Only)
Table 14.2.1.7	Central Corneal Thickness (µm) as Assessed by Ultrasound Pachymetry by Visit	Modified Intent-to-Treat Population (Observed Data Only)

Table 14.2.2.1	Change from Baseline in Best Corrected Visual Acuity using ETDRS Method by Visit	Modified Intent-to-Treat Population (Observed Data Only)
Table 14.2.2.2	Change from Baseline in Best Corrected Visual Acuity using ETDRS Method by Visit	Per Protocol Population (Observed Data Only)
Table 14.2.2.3	Best Corrected Visual Acuity using ETDRS Method by Visit	Modified Intent-to-Treat Population (Observed Data Only)
Table 14.2.3.1.1	Proportion of Subjects Who Gained 15 Letters or More in BCVA using ETDRS Method by Visit	Modified Intent-to-Treat Population (Observed Data Only)
Table 14.2.3.1.2	Proportion of Subjects Who Gained 15 Letters or More in BCVA using ETDRS Method by Visit	Per Protocol Population (Observed Data Only)
Table 14.2.3.2.1	Proportion of Subjects Who Gained 10 Letters or More in BCVA using ETDRS Method by Visit	Modified Intent-to-Treat Population (Observed Data Only)
Table 14.2.3.2.2	Proportion of Subjects Who Gained 10 Letters or More in BCVA using ETDRS Method by Visit	Per Protocol Population (Observed Data Only)
Table 14.2.3.3.1	Proportion of Subjects Who Gained 5 Letters or More in BCVA using ETDRS Method by Visit	Modified Intent-to-Treat Population (Observed Data Only)
Table 14.2.3.3.2	Proportion of Subjects Who Gained 5 Letters or More in BCVA using ETDRS Method by Visit	Per Protocol Population (Observed Data Only)
Table 14.2.4.1	Proportion of Subjects with Complete Resolution of Corneal Edema by Visit	Modified Intent-to-Treat Population (Observed Data Only)
Table 14.2.4.2	Proportion of Subjects with Complete Resolution of Corneal Edema by Visit	Per Protocol Population (Observed Data Only)
Table 14.2.5	Change from Baseline in Central Corneal Thickness ( $\mu\text{m}$ ) as Assessed by Pentacam by Visit	Modified Intent-to-Treat Population (Observed Data Only)
Table 14.2.6	Change from Baseline in V-FUCHS Factor Score by Visit	Modified Intent-to-Treat Population (Observed Data Only)
Table 14.2.7	Proportion of Subjects with Complete Resolution of Epithelial Edema by Visit	Modified Intent-to-Treat Population (Observed Data Only)
Table 14.3.1	Overall Summary of Treatment-Emergent Adverse Events by Treatment Group	Safety Population
Table 14.3.2.1	Ocular Treatment-Emergent Adverse Events by System Organ Class and Preferred Term	Safety Population
Table 14.3.2.2	Non-Ocular Treatment-Emergent Adverse Events by System Organ Class and Preferred Term	Safety Population

Table 14.3.2.3	Ocular Treatment-Emergent Adverse Events Related or Possibly Related to Study Medication by System Organ Class and Preferred Term	Safety Population
Table 14.3.2.4	Non-Ocular Treatment-Emergent Adverse Events Related or Possibly Related to Study Medication by System Organ Class and Preferred Term	Safety Population
Table 14.3.2.5	Serious Treatment-Emergent Adverse Events by System Organ Class and Preferred Term	Safety Population
Table 14.3.2.6	Serious Treatment-Emergent Adverse Events Related or Possibly Related to Study Medication by System Organ Class and Preferred Term	Safety Population
Table 14.3.2.7	Ocular Treatment-Emergent Adverse Events by System Organ Class, Preferred Term, and Maximum Severity	Safety Population
Table 14.3.2.8	Non-Ocular Treatment-Emergent Adverse Events by System Organ Class, Preferred Term, and Maximum Severity	Safety Population
Table 14.3.3.1	Best Corrected Visual Acuity (BCVA) Using ETDRS Method by Treatment and Visit	Safety Population
Table 14.3.3.2.1.1	Shifts in Biomicroscopy from Baseline by Treatment and Visit – Study Eye	Safety Population
Table 14.3.3.2.1.2	Shifts in Biomicroscopy from Baseline by Treatment and Visit – Fellow Eye	Safety Population
Table 14.3.3.2.2	Number and Percentage of Subjects with at Least a One Severity Grade Increase from Baseline Biomicroscopy Findings	Safety Population
Table 14.3.3.2.3	Number and Percentage of Subjects with Biomicroscopy Findings Judged Clinically Significant by the Investigator	Safety Population
Table 14.3.3.3	Mean Intraocular Pressure (IOP) by Treatment and Visit	Safety Population
Table 14.3.3.4.1	Shifts in Ophthalmoscopy from Baseline by Treatment and Visit - Study Eye	Safety Population
Table 14.3.3.4.2	Shifts in Ophthalmoscopy from Baseline by Treatment and Visit - Fellow Eye	Safety Population
Table 14.3.3.5	Vital Signs by Treatment and Visit	Safety Population

## 19. Listings

Listing Number	Title	Population
Listing 16.1.7	Randomization Schedule	All Randomized Subjects
Listing 16.2.1.1	Subject Disposition	All Randomized Subjects
Listing 16.2.1.2	Subject Disposition	Screen Failed Subjects
Listing 16.2.2	Protocol Deviations	All Randomized Subjects
Listing 16.2.3	Analysis Populations	All Randomized Subjects

Listing 16.2.4.1	Demographics	All Randomized Subjects
Listing 16.2.4.2	Childbearing Potential	All Randomized Female Subjects Only
Listing 16.2.4.3	Ocular Medical History	All Randomized Subjects
Listing 16.2.4.4	Non-Ocular Medical History	All Randomized Subjects
Listing 16.2.4.5	Ocular Surgery Laser Procedure	All Randomized Subjects
Listing 16.2.4.6	Prior and Concomitant Medications	All Randomized Subjects
Listing 16.2.5	Study Drug and Artificial Tears Assignment	All Randomized Subjects
Listing 16.2.6.1	Central Corneal Thickness (CCT) by Ultrasound Pachymetry	All Randomized Subjects
Listing 16.2.6.2	Best Corrected Visual Acuity by ETDRS	All Randomized Subjects
Listing 16.2.6.3	Biomicroscopy	All Randomized Subjects
Listing 16.2.6.4	Tomography	All Randomized Subjects
Listing 16.2.6.5.1	Visual Function and Corneal Health Status (V-FUCHS) – Visual Acuity Factor	All Randomized Subjects
Listing 16.2.6.5.2	Visual Function and Corneal Health Status (V-FUCHS) – Glare Factor	All Randomized Subjects
Listing 16.2.7.1	All Adverse Events	All Randomized Subjects
Listing 16.2.7.2	Serious Adverse Events	All Randomized Subjects
Listing 16.2.7.3	Adverse Events Leading to Study Medication Discontinuation	All Randomized Subjects
Listing 16.2.7.4	Adverse Events Leading to Death	All Randomized Subjects
Listing 16.2.8	Pregnancy Test	All Randomized Female Subjects with Childbearing Potential
Listing 16.2.9	Intraocular Pressure (IOP)	All Randomized Subjects
Listing 16.2.10	Ophthalmoscopy	All Randomized Subjects
Listing 16.2.11	Vital Signs	All Randomized Subjects

